5.2 Secondary outcomes

The secondary outcomes of this study measure the respective secondary objectives stated in section 2.2.

- i. To determine the rate of intubation - i.e. estimate the proportion of children randomised to the intervention or control who need intubation (Group A) or re-intubation (Group B) within 72 hours of randomisation
- ii. To determine the rate of treatment failure - i.e. estimate the proportion of children randomised to the intervention or control who fail the assigned treatment and require either crossover or escalation to other forms of ventilation within 72 hours of randomisation
- iii. To assess safety – i.e. estimate the number of children who experience pre-specified adverse events i.e.
 - a. Pneumothorax
 - b. Pneumomediastinum
 - c. Subcutaneous emphysema
 - d. Abdominal distension
 - e. Nasal or facial trauma
 - f. Facial trauma
 - g. Facial thermal injury
 - h. Respiratory/Cardiac arrest
 - i. Aspirationduring the period they were receiving non-invasive respiratory support
- iv. To assess physiological effects – i.e. estimate changes in:
 - a. oxygenation
 - b. pCO₂ levels

- c. heart rate
 - d. respiratory rate
 - e. and work of breathing
- in the first 24 hours after the initiation of CPAP/HFNC
- v. To assess effects on patient outcome – i.e. estimate:
 - a. length of PICU stay
 - b. hospital stay
 - c. length of invasive ventilation
 - d. length of non-invasive support
 - e. ventilator-free days at day 28
 - f. PICU mortality
 - g. hospital mortality

6. Power calculation

Since this is a feasibility study, no formal sample size calculations was performed. Based on analysis of audit data, we expect around 250 eligible patients over the 6-month period at the three sites. Assuming a 50% recruitment rate, we will have recruited 120 study patients (around 40 patients in Group A). Data from the literature suggests a 20% rate of intubation for Group A (i.e. we expect to see eight intubation events), and a 10% rate of re-intubation for Group B (i.e. we expect to see eight re-intubation events).

7. Statistical methods

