- iii. Mean (SD) modified COMFORT score at individual time points by tolerating allocated treatment (Yes or No) at that time point
- iv. Mean (SD) across patients of the mean within-patient modified COMFORT score for patients with a highest level of respiratory distress of moderate or severe compared with those with a highest level of none or mild

Assessment of the suitability of the PSS:PICU will be evaluated by:

- i. Number and percentage of parents returning a completed questionnaire
- ii. Number and percentage of returned questionnaires with:
 - a. All questions completed
 - b. >90% of questions completed

The number and percentage of patients experiencing treatment failures, defined as crossover or escalation to other forms of ventilation within 72 hours of randomisation, will be reported for each group. Breakdowns of the numbers of crossovers and escalation (by level of respiratory support) will be reported.

The number and percentage of patients experiencing each pre-specified adverse event (plus any other adverse events as reported) will be summarised for each treatment group. Numbers of severe adverse events and their reported relatedness to treatment will be reported in text.

The physiological effects of treatment will be presented graphically by plotting the mean \pm SD of each physiological parameter at the time points recorded (Hours 0, 1, 2, 3, 4, 5, 6, 12, 24, 36, 48 and 72).

A comparison of outcomes by treatment group will be reported for the following outcome measures:

- i. Intubation within 72 hours
- ii. Treatment failure within 72 hours (separately for crossover and escalation patients)
- iii. Length of PICU stay
- iv. Length of hospital stay
- v. Length of invasive ventilation
- vi. Length of non-invasive support
- vii. Ventilator-free days at day 28
- viii. PICU mortality
- ix. Hospital mortality

Binary outcomes will be reported as the number and percentage in each group, the risk ratio and absolute risk reduction with 95% confidence intervals. Continuous outcomes will be reported as the mean (SD) and median (IQR) in each group and the difference in means with 95% confidence interval.

Differences in treatment effect between Group A and Group B for all outcome measures will be tested as interaction tests (Mantel-Haenszel tests for binary outcomes, interaction terms in linear regression models for continuous outcomes) and presented as forest plots.

9. Reporting conventions

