n: Number of patients; %: Percentage of patients; N: Total number of patients;
SD: Standard deviation; IQR: Inter-quartile range

Figure 1: Study flow diagram

CONSORT flow diagram

Figure 2: Flow rate/pressure over time

Mean (SD) at Hours 0, 1, 2, 3, 4, 5, 6, 12, 24, 36, 48 and 72. Panels for:

- Flow rate (<10 kg vrs ≥10 kg - l kg⁻¹ min⁻¹) – HFNC group
- Pressure (cmH₂O) – CPAP group

Figure 3: Physiology/comfort/respiratory distress over time

Mean (SD), unless indicated, by treatment group at Hours 0, 1, 2, 3, 4, 5, 6, 12, 24, 36, 48 and 72. Panels (Group A and Group B) for:

- Respiratory rate (breaths min⁻¹)
- Heart rate (beats min⁻¹)
- SpO₂ (%)
- PaO₂ (kPa)
- FiO₂
- pH
- pCO₂ (kPa)
- Modified COMFORT score
- Percentage with Moderate/Severe respiratory distress

Numbers at the foot of each figure will indicate the number of patients with measurements at each timepoint.

Figure 4: Forest plot of outcomes

All outcomes from Table 7 reported for Group A, Group B and overall with test of interaction. Panels for (A) binary outcomes (risk ratio); and (B) continuous outcomes (difference in means).

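### The overall HFNC v CPAP effects in Section 8, Table 7 and Figure 4 read as unadjusted for Group A/B; stratifying them by group is a small gain in precision that needs no new data

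*SAP*

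**What the plan says.** SAP Section 8 sets out the comparison of the two arms. For binary outcomes: "Binary outcomes will be reported as the number and percentage in each group, the risk ratio and absolute risk reduction with 95% confidence intervals". For continuous outcomes it adds "the difference in means with 95% confidence interval" to the summaries by arm. It names no stratification factor or covariate for these effects. Table 7 in Section 10 has one HFNC v CPAP effect and one P value per outcome.

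Group A/B enters the outcome comparison in two ways only: through the interaction tests (Mantel-Haenszel for binary outcomes, interaction terms in linear regression for continuous ones), and through separate rows in Figure 4: "All outcomes from Table 7 reported for Group A, Group B and overall with test of interaction". How the overall row is formed is not stated.

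Section 6 expects "a 20% rate of intubation for Group A" and half that, 10%, for re-intubation in Group B. The SAP does not state the allocation ratio or whether randomisation was stratified by group.

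**The concern.** Group A/B is the plan's own divider of risk. It is fixed at entry, tabulated by arm in Table 1b, and already used in the interaction models. As naturally read, the overall effect ignores it. There are two possible consequences, depending on how children were allocated:

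- **Allocation not stratified by group.** The share of Group A children can differ between arms by chance. Part of that difference then appears in the overall estimate as noise. The overall row of Figure 4 need not be a weighted average of the two rows beside it, and in an unlucky draw it can lie outside both.
- **Allocation stratified by group.** The arms are balanced, but an interval that ignores group counts the variation between groups as error and is slightly too wide.

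What is at stake is some precision in a trial of 120, and whether the overall row of the forest plot agrees with its subgroup rows.

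**Working it through.** **Inputs from Section 6.** 120 children, about 40 in Group A, hence about 120 − 40 = 80 in Group B. Expected intubation is 20% in A and 10% in B. Assumed, because the SAP does not state it: 1:1 allocation, 60 per arm.

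**The plan's own figures.** 40 × 0.20 = 8 events in A and 80 × 0.10 = 8 in B. Both match Section 6. The pooled risk is 16/120 = 13.3%.

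**Size of chance imbalance without stratified allocation.** The Group A count in one arm is hypergeometric, with mean 20 and SD = √(60 × 1/3 × 2/3 × 60/119) = 2.59. Its 95% range is 15 to 25. A 25/15 split or worse, in either direction, occurs in about 8% of trials.

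**Effect of a 25/15 split when treatment does nothing.**
- Arm 1: (25 × 0.20 + 35 × 0.10)/60 = 14.2%
- Arm 2: (15 × 0.20 + 45 × 0.10)/60 = 12.5%
- Difference 1.7 points, risk ratio 1.13, while the risk ratio within each group is 1.00.

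**Compared with sampling error.**
- Unadjusted SE of the risk difference: √(2 × 0.1333 × 0.8667/60) = 6.21 points, so the 95% half-width is 1.96 × 6.21 = 12.2 points.
- At 8 v 8 events, the SE of the log risk ratio is √(2 × (1/8 − 1/60)) = 0.465, so the interval is 0.40 to 2.49.
- The SD of the shift due to group mix is 0.10 × 2 × 2.59/60 = 0.86 points. Its share of the variance is (0.86/6.21)² = about 2%.

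**Gain from stratifying, intubation.** The within-group variance is (1/3) × 0.16 + (2/3) × 0.09 = 0.1133. The stratified SE is √(2 × 0.1133/60) = 6.15 points, about 1% smaller than 6.21. In 200,000 simulated trials under no effect and unstratified allocation, the SDs were 6.21 points unadjusted and 6.17 points Mantel-Haenszel. Both estimators were centred on zero. In one and the same trial they differed by 0.7 points on average, and by less than 2.3 points in 95% of trials.

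**Gain from stratifying, continuous outcomes.** The SAP gives no difference between Groups A and B for any of these, so take d = 0.5 to 1.0 within-group SD as an assumption. The unadjusted SD is inflated by √(1 + (1/3)(2/3)d²): 1.027 at d = 0.5 and 1.106 at d = 1.0. Adjusting for group therefore narrows the interval by 1 − 1/1.027 = 2.7% and 1 − 1/1.106 = 9.5%. A 25/15 split would shift the unadjusted difference by (10/60) × d, which is 0.08 to 0.17 SD.

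**If allocation was stratified by group.** For intubation the unadjusted 95% interval covers 95.2%, since 1.96 × 6.21/6.15 = 1.98. For continuous outcomes under the same assumed d, coverage is about 96% to 97%.

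**The case against.** The strongest case against is that an unadjusted estimate fixed in advance is a legitimate choice, and that on the one outcome with figures in the SAP the difference is negligible: 1% in SE, and a 1.7-point shift in an unlucky draw against a half-width of 12 points. The larger gains rest on a group difference that the SAP does not give. The primary outcomes are feasibility measures, the group-specific effects are shown beside the overall row, and Table 1b lets a reader see any imbalance. All of this stands, and it keeps the point minor.

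Two further objections limit the wording:

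- The SAP never uses the word crude or unadjusted. That is the natural reading of a difference in means printed beside the arm means, but it remains a reading. A Mantel-Haenszel routine run for the interaction test could also supply a pooled effect for Figure 4. That possibility does not remove the point: Figure 4 and Table 7 could then carry two different overall effects for one binary outcome.
- A reader might infer that chance imbalance in group mix biases the overall effects. The documents do not support this. Over repeated randomisation the unadjusted comparison is centred on the true effect, and its interval already allows for this noise on average. Imbalance of any size also requires allocation that was not stratified by group, which is a matter for the protocol, and that is not at hand.

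**Conclusion.** The point holds as a minor improvement. As naturally read, the overall effects ignore an entry factor for which the plan itself expects a twofold difference in intubation. The estimates are unbiased, and the loss is one of precision: about 1% in SE for intubation, and about 3% to 10% in interval width for a continuous outcome only if the groups differ by 0.5 to 1.0 SD. All figures assume 60 per arm and the group sizes in Section 6; the intubation figures also use its two rates. The conclusion does not depend on how allocation was done. Without stratification by group, adjustment removes noise; with it, adjustment gives an interval of the right width. The case for acting is that group is already recorded and that Figure 4's overall row would then agree with its subgroup rows and with Table 7.

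**What to change.** State in Section 8 that the overall effects in Table 7 and Figure 4 are stratified by Group A/B:

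- Binary outcomes: Mantel-Haenszel pooled risk ratio and risk difference across the two groups, with 95% confidence intervals.
- Continuous outcomes: the treatment coefficient from a linear model with a term for group.
- The same overall estimate in both displays.
- Crude n (%) and mean (SD) by arm kept as they are.

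The cost is a sentence or two of SAP wording and a group term in analyses that already use group for the interaction tests. No new data are needed.

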The following reporting conventions will be used for the SAP. These conventions will enhance the review of the study report and help to standardize presentation with common notations.

- i. Sample sizes will be presented for each treatment group as totals in the column header as “(N = xxx)”, where appropriate.
- ii. Sample sizes shown with summary statistics are the samples sizes (n) of patients with non-missing values.
- iii. All summaries for categorical variables will include all categories that were available and will not be restricted to those with at least one response.

- iv. Summaries for continuous variables that are approximately normally distributed will be reported as n, mean and standard deviation (SD).
- v. Summaries for continuous variables that are not normally distributed will be reported as n, median and quartiles.
- vi. All percentages will be rounded and reported to a single decimal place (xx.x%). A percentage of 0% will be reported as “0%”; a percentage of 100% will be reported as “100%”.
- vii. Summaries that include P-values will report the P-value to three decimal places with a leading zero (0.xxx). P-values of less than 0.0005 will be reported as “<0.001” not “0.000”.
- viii. Missing values for both numeric and string variables will be presented as dashes (“---”) or as “Not available” / “Not applicable” / “Not reported” (as appropriate) in tables or data listings.

10. Appendix – proposed tables and figures

Table 1a: Number of patients screened, eligible, consented and randomised by site

Variables	Site A	Site B	Site C	Total
Number screened, N				
Group A	XX	XX	XX	XXX
Group B:	XX	XX	XX	XXX
Planned	XX	XX	XX	XXX
Rescued	XX	XX	XX	XXX
Total	XX	XX	XX	XXX
Number of eligible patients, n (% of screened)				
Group A	XX	XX	XX	XXX
Group B:	XX	XX	XX	XXX
Planned	XX	XX	XX	XXX
Rescued	XX	XX	XX	XXX
Total	XX	XX	XX	XXX
Number of patients randomised, n (% of eligible)				
Group A	XX	XX	XX	XXX
Group B:	XX	XX	XX	XXX
Planned	XX	XX	XX	XXX
Rescued	XX	XX	XX	XXX
Total	XX	XX	XX	XXX
Consent obtained, n (% of randomised)				
Group A	XX	XX	XX	XXX
Group B:	XX	XX	XX	XXX
Planned	XX	XX	XX	XXX
Rescued	XX	XX	XX	XXX
Refused consent, n (% of randomised)				
Group A	XX	XX	XX	XXX
Group B:	XX	XX	XX	XXX
Planned	XX	XX	XX	XXX
Rescued	XX	XX	XX	XXX
Total	XX	XX	XX	XXX
Death prior to consent, n (% of randomised)				
Group A	XX	XX	XX	XXX
Group B:	XX	XX	XX	XXX
Planned	XX	XX	XX	XXX
Rescued	XX	XX	XX	XXX
Total	XX	XX	XX	XXX
Discharged prior to consent, n (% of randomised)				

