	Group A	XX (XX.X)	XX (XX.X)
	Group B	XX (XX.X)	XX (XX.X)
	Total	XX (XX.X)	XX (XX.X)
Subcutaneous emphysema, n (%)			
	Group A	XX (XX.X)	XX (XX.X)
	Group B	XX (XX.X)	XX (XX.X)
	Total	XX (XX.X)	XX (XX.X)
Abdominal distension, n (%)			
	Group A	XX (XX.X)	XX (XX.X)
	Group B	XX (XX.X)	XX (XX.X)
	Total	XX (XX.X)	XX (XX.X)
Nasal trauma, n (%)			
	Group A	XX (XX.X)	XX (XX.X)
	Group B	XX (XX.X)	XX (XX.X)
	Total	XX (XX.X)	XX (XX.X)
Facial trauma, n (%)			
	Group A	XX (XX.X)	XX (XX.X)
	Group B	XX (XX.X)	XX (XX.X)
	Total	XX (XX.X)	XX (XX.X)
Facial thermal injury, n (%)			
	Group A	XX (XX.X)	XX (XX.X)
	Group B	XX (XX.X)	XX (XX.X)
	Total	XX (XX.X)	XX (XX.X)
Respiratory/Cardiac arrest, n (%)			
	Group A	XX (XX.X)	XX (XX.X)
	Group B	XX (XX.X)	XX (XX.X)
	Total	XX (XX.X)	XX (XX.X)
Aspiration, n (%)			
	Group A	XX (XX.X)	XX (XX.X)
	Group B	XX (XX.X)	XX (XX.X)
	Total	XX (XX.X)	XX (XX.X)
Other ^a , n (%)			
	Group A	XX (XX.X)	XX (XX.X)
	Group B	XX (XX.X)	XX (XX.X)
	Total	XX (XX.X)	XX (XX.X)

n: Number of patients; %: Percentage of patients; N: Total number of patients

^a Other reported adverse events were...

Table 7: Comparison of outcomes by treatment group

Outcome	HFNC	CPAP	Effect estimates (95% CI)	P value
	N = XXX	N = XXX		
Intubation within 72h				
n (%)	XX (XX.X)	XX (XX.X)	Risk ratio: X.XX (X.XX, X.XX) Absolute risk reduction: XX.X (XX.X, XX.X)	0.XXX
Treatment failure within 72h				
n (%)	XX (XX.X)	XX (XX.X)	Risk ratio: X.XX (X.XX, X.XX) Absolute risk reduction: XX.X (XX.X, XX.X)	0.XXX
Length of PICU stay from randomisation (days):				
Mean (SD)	X.X (X.X)	X.X (X.X)	Mean difference: X.X (X.X,X.X)	0.XXX
Median (IQR)	X.X (X.X,X.X)	X.X (X.X,X.X)		
Length of hospital stay (days)				
Mean (SD)	X.X (X.X)	X.X (X.X)	Mean difference: X.X (X.X,X.X)	0.XXX
Median (IQR)	XX (XX,XX)	XX (XX,XX)		
Length of invasive ventilation (days)				
Mean (SD)	X.X (X.X)	X.X (X.X)	Mean difference: X.X (X.X,X.X)	0.XXX
Median (IQR)	XX (XX,XX)	XX (XX,XX)		
Length of non-invasive respiratory support (days)				
Mean (SD)	X.X (X.X)	X.X (X.X)	Mean difference: X.X (X.X,X.X)	0.XXX
Median (IQR)	XX (XX,XX)	XX (XX,XX)		
Ventilator-free days at day 28				
Mean (SD)	X.X (X.X)	X.X (X.X)	Mean difference: X.X (X.X,X.X)	0.XXX
PICU mortality				
n (%)	XX (XX.X)	XX (XX.X)	Risk ratio: X.XX (X.XX, X.XX) Absolute risk reduction: XX.X (XX.X, XX.X)	0.XXX
Hospital mortality				
n (%)	XX (XX.X)	XX (XX.X)	Risk ratio: X.XX (X.XX, X.XX) Absolute risk reduction: XX.X (XX.X, XX.X)	0.XXX

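### The interaction test for binary outcomes is named only as Mantel-Haenszel, which permits a test of the common effect instead of a test of the Group A/B difference

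*SAP*

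**What the plan says.** Section 8 sets the question as "Differences in treatment effect between Group A and Group B for all outcome measures". It says these "will be tested as interaction tests (Mantel-Haenszel tests for binary outcomes, interaction terms in linear regression models for continuous outcomes"), with the results shown as forest plots. The appendix entry for Figure 4 repeats the aim: "All outcomes from Table 7 reported for Group A, Group B and overall with test of interaction". Neither place says whether the Mantel-Haenszel statistic is the association test or the homogeneity test. The SAP uses neither the word homogeneity nor heterogeneity, and the software section names Stata but no command.

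For the treatment comparison itself, Section 8 plans "the risk ratio and absolute risk reduction with 95% confidence intervals" for binary outcomes and a difference in means with its interval for continuous ones. No adjustment and no test is mentioned. The shell headed "Table 7: Comparison of outcomes by treatment group" nevertheless has a P value cell for each of nine outcomes (four binary, five continuous). The reporting conventions in Section 9 give only a rounding rule for P values. On size, Section 6 states: "Since this is a feasibility study, no formal sample size calculations was performed".

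**The concern.** The null hypothesis of the usual Mantel-Haenszel test is that the treatment effect, pooled over strata, is absent. An interaction test has a different null: that the effect is the same in both strata. If the first were run and printed beside the forest plot as the test of interaction, a benefit shared equally by step-up and step-down patients could be reported as a difference between them. A real reversal of effect could pass unnoticed.

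The SAP states in its introduction that it is fixed before outcome data are inspected, so that analysis choices do not depend on the data. Leaving open two tests that can give opposite answers works against that aim. Continuous outcomes are not affected, because the same sentence names a regression interaction term for them.

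**Working it through.** **Inputs from SAP Section 6.** 120 patients, about 40 of them in Group A, so 120 − 40 = 80 in Group B. Intubation is expected in 20% of Group A and re-intubation in 10% of Group B.

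**The plan's own figures.** 40 × 0.20 = 8 events and 80 × 0.10 = 8 events, as stated; 16 in total.

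**Assumptions not in the SAP.** 1:1 allocation within each group (20/20 and 40/40) and a two-sided 5% level, used only to express rejection rates.

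**Two statistics.** For stratum *i* with *a* events among *n*₁ in one arm, *c* among *n*₀ in the other, *m* = *a* + *c* and *N* = *n*₁ + *n*₀:
- Common effect: [Σ(*a* − *m n*₁/*N*)]² / Σ[*n*₁*n*₀*m*(*N* − *m*) / (*N*²(*N* − 1))], on 1 df.
- Homogeneity: Σ(log RRᵢ − log RR_MH)² / vᵢ, with vᵢ = 1/*a* − 1/*n*₁ + 1/*c* − 1/*n*₀, on 1 df.

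**Worked tables, 16 events each.**
- *Same effect* (A 2/20 v 6/20, B 2/40 v 6/40; risk ratio 0.33 in both). Common effect: (−2 − 2)² / (1.641 + 1.823) = 4.62, P = 0.032. Homogeneity: 0, P = 1.00.
- *Opposite effects* (A 1/20 v 7/20, B 7/40 v 1/40). Common effect: (−3 + 3)² / 3.464 = 0, P = 1.00. Homogeneity: log risk ratios −1.946 and +1.946, variances 1.043 and 1.093, pooled log 0; 3.787/1.043 + 3.787/1.093 = 7.10, P = 0.008.

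**Simulated rejection rates at the planned size.**

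| Truth | Common-effect test | Homogeneity test |
|---|---|---|
| Halved in both (A 20% to 10%, B 10% to 5%) | 23% | about 1% |
| Opposite (A 30% to 10%, B 10% to 20%) | 4% | about 41% |

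The homogeneity column uses a Wald test on the difference in log risk ratios with 0.5 added to every event count and arm size. Adding the correction only where a zero occurs, or using Mantel-Haenszel weighting, gives 1% to 2% and 44% to 46%. The contrast does not depend on that choice.

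**Information available.** With events at the SAP's rates and no effect (4/20 v 4/20 and 4/40 v 4/40), the standard error of the log ratio of risk ratios is √[2(1/4 − 1/20) + 2(1/4 − 1/40)] = √0.85 = 0.922. The 95% CI is exp(±1.96 × 0.922) = 0.16 to 6.1.

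**Gain from adjusting overall estimates for Group A/B.** The group shares are 1/3 and 2/3.
- Intubation: between-group variance (1/3)(2/3)(0.20 − 0.10)² = 0.00222. Total variance 0.1333 × 0.8667 = 0.1156. The ratio is about 2%.
- Continuous outcome with an assumed 0.5 SD difference between groups: (2/9)(0.25) = 0.0556, and 0.0556/1.0556 is about 5%.

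**The case against.** The strongest reply is that the sentence fixes its own hypothesis. It speaks of differences in effect between groups, calls the tests interaction tests, and pairs them with regression interaction terms. A Mantel-Haenszel homogeneity test exists, and a competent analyst would probably choose it. This stands. A reader might infer that the SAP commits to the wrong test, and the document does not support that. What remains is that the unqualified name ordinarily denotes the other test and nothing in the SAP excludes it.

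A reader might also infer that a wrong answer would decide whether the full trial treats step-up and step-down patients as one population or two. The SAP contains no such rule. Its primary objectives concern eligibility, consent, recruitment, delivery of the protocol and the two instruments.

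A third tempting reading is that P values in a trial without a formal sample size calculation are an error that will generate false claims. The SAP sets no significance level and attaches no efficacy conclusion to these secondary outcomes, which are clearly correlated, so no error rate can be calculated from it. Only two of the planned tests, the intubation comparison and its interaction, rest on the 16 intubation events. The defect that can be shown is narrower: Table 7 has P values that Section 8 does not plan and for which no test is named.

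Finally, unadjusted overall estimates are not wrong, and the randomisation scheme may be set out in the protocol. Adjustment is an improvement, not a correction.

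**Conclusion.** The point holds as a specification fault. The interaction test for the four binary outcomes is named in a way that, taken literally, selects a test of the wrong hypothesis: 23% against about 1% rejection when both groups benefit equally, and 4% against about 41% when effects are opposite. These rates rest on 1:1 allocation within groups, a 5% level and the stated scenarios. The halving scenario starts from the SAP's own event rates; the opposite-effects scenario is illustrative.

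Even the right test will say little here, since the interval for the ratio of risk ratios spans roughly 0.16 to 6.1. That argues for showing the interval. No primary outcome or feasibility conclusion is affected. Severity: should-fix.

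**What to change.** 1. **Name the test.** In Section 8, specify the Mantel-Haenszel test of homogeneity of the risk ratio, or a treatment-by-group term in a risk-ratio model. Breslow-Day does not fit, because it concerns odds ratios while the SAP reports and plots risk ratios. Report the ratio of the two risk ratios with a 95% CI, and omit the test when any stratum-arm cell has no events.
2. **Adjust the overall effects in Table 7 for Group A/B.** Use the Mantel-Haenszel risk ratio and risk difference for binary outcomes, and linear regression with group as a covariate for continuous ones. The gain is small for intubation and somewhat larger for continuous outcomes that differ between groups.
3. **Reconcile Section 8 with the Table 7 shell.** Either name the tests behind the P values or remove the column; removal is optional. Label Table 7 and Figure 4 as exploratory.

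The cost is SAP wording and a table shell, with no new data. The one practical loss is that the zero-cell rule will sometimes leave no interaction test: for intubation, in about 5% of simulated trials with no effect and about 25% if rates are halved, and probably more often for mortality if deaths are rare.
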